14.7 Data Monitoring Committee

There will be no data monitoring committee.

14.8 Unanticipated Problems

All adverse events will be recorded and will be reported appropriately as outlined in the REB guidelines.

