3. EXPECTED RISKS/ BENEFITS

3.1 Expected Risks

Low intensity aerobic and balance exercise poses minimal risk for healthy individuals. Like all types of exercise, there is a slight risk of sustaining a musculoskeletal injury such as a sprain or strain. There is a small risk, however, when performing aerobic and balance exercises while experiencing PCS; participants may see an increase or worsening of his/her symptoms. In order to minimize this risk, exercise will begin at a very low intensity and gradually increase. All exercise sessions will be monitored by a research team member to ensure that the session is being completed at the proper intensity. Should a participant report any PCS during a session, the session will be stopped immediately. Furthermore, to ensure that participants are healthy enough to participate in exercise, all participants will be medically cleared by [name] prior to participating in the study.

There is a minor risk that, when using the driving simulator, participants may experience symptoms such as nausea or dizziness. Breaks will be allowed during the assessment in an effort to prevent this. Water will also be readily available during the assessment should the participant require it. If a participant experiences any of these symptoms and is unable to continue, the session will end.

Physical and cognitive assessment, neuroimaging, and biomarker assessment should pose minimal risk to participants.

There is a minor social risk with respect to confidentiality. This risk will be minimized by ‘de-identifying’ the personal information with codes. All names will be removed from data/samples. All data will be stored in an encrypted file on the secure Sync.com account on a password-protected computer in a locked office at LU. Any hard copies of data such as screening checklists or the IPAQ will be coded and stored in a locked filing cabinet in a secure office at LU ([name] current office, SB 1007). All saliva samples will be coded and stored in [name] secure lab.

The results of this study will be published with aggregate data, that is, data which is combined and summarized so that no individual participant can be identified.

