6.4 Procedures for Participant Enrolment /Allocation /Randomization

To achieve adequate enrolment, recruitment flyers will be placed at several locations and clinics around Thunder Bay. Once informed consent has been obtained, and the potential participant has been deemed eligible through the screening process, age and sex of the participant will be used to randomly assign the participant to an intervention group through a process called minimization. This process ensures group sizes are equal and eliminates potential bias that may be introduced which is important for clinical research of small sizes. The NOSM research assistant would then communicate the enrolment and group assignment to [name] who will administer the AET intervention. The SC intervention will continue under the supervision of the participant's healthcare provider. Participants will be assigned a code number by the research assistant to ensure confidentiality is maintained during the transfer of data or samples between locations.

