duration, surface, and whether the participant's eyes are open or closed. For weeks one and two participants will perform the exercises with his/her eyes open; participants will perform each exercise for 15 seconds on a firm surface in week one, and on a low density foam block in week two. In weeks three and four, participants will perform the exercises with his/her eyes closed; exercises in week three will be performed on a firm surface, while week four will be performed on a low density foam block. Duration will be increased to twenty seconds per exercise for weeks three and four. Weeks four to eight will follow the same eyes open/closed and surface progression as weeks one to four; eyes open for weeks five and six, eyes closed for weeks seven and eight. Exercises will be performed on a firm surface in weeks five and seven, and on a low density foam block in weeks six and eight. Participants will perform each exercise for 35 seconds in weeks five and six, and 40 seconds in weeks seven and eight. Following the completion of the aerobic and balance components of the session, participants will complete a cool down consisting of a series of static stretches. Each session will conclude after the completion of the cooldown.

After completion of 24 sessions (eight weeks x three-one hour sessions per week), participants will repeat the procedures for the previously described baseline assessments. Similarly, HC and SC participants will complete the baseline assessments again after eight weeks.

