12.4 Premature discontinuation or termination of the study

The study sponsor/investigator and the Research Ethics Board reserve the right to terminate this research study at any time. Reasons for termination include but are not limited to:

The occurrence of adverse events poses a potential health risk for participants;

Unsatisfactory participant enrollment;

Investigator request to withdraw from study;

Noncompliance with the protocol or regulatory guidelines are not being followed;

REB decision to terminate or suspend approval for the investigation or Investigator.

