13. QUALITY CONTROL AND QUALITY ASSURANCE

We are able to track adherence to the protocol because the intervention requires a visit which is documented in the data abstraction form. All data will be translated into the data abstraction forms. To promote data quality, all team members will be trained in their duties. All questionnaires to be used are valid (see Section 7.2).

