16.4 Data abstraction form

Participant Number: _____

Consent Date:

| | |
|--------------------------|--|
| Sex (male/female) | |
| Height (cm) | |
| Weight (kg) | |
| Age (in years) | |
| | |
| Date of injury | |
| Date of first assessment | |

Past Medical History

- Concussion
- Traumatic brain injury
- Migraine
- ADHD
- Motion sickness

(Y/N)

| |
|--|
| |
| |
| |
| |
| |

How many?

| |
|--|
| |
|--|

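### Adverse events are looked for unequally by arm (24 monitored AET sessions, no scheduled SC contact), with no schedule row, form field or named reviewer, so any between-arm harms summary would be open to ascertainment bias

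*Combined protocol and SAP*

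**What the plan says.** Section 14.8 is a single sentence: "All adverse events will be recorded and will be reported appropriately as outlined in the REB guidelines". It does not define an event, say how or how often participants are asked, or name who is responsible.

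Section 3.1 names the main risk of exercising with post-concussion symptoms: "participants may see an increase or worsening of his/her symptoms". The same section has a team member monitor every exercise session and has the session stopped if symptoms are reported.

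Contact during the eight weeks differs by arm. For AET, section 7.2 places the post assessments "After completion of 24 sessions (eight weeks x three-one hour sessions per week"). For SC, section 6.4 says "The SC intervention will continue under the supervision of the" participant's own provider, and section 5.1 sets that period at eight weeks. HC participants receive no intervention. The Garmin unit given to both concussion arms (5.1) tracks activity and heart rate; it does not ask about symptoms. The 7.1 schedule has no row for adverse events in any arm.

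On recording, section 13 relies on the fact that "the intervention requires a visit which is documented in the data abstraction form" and says all data are carried into these forms. The form in 16.4 holds consent date, demographics, date of injury, "Date of first assessment" and past medical history.

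On review, section 12.4 lists "The occurrence of adverse events poses a potential health risk for participants" as a reason to terminate. Section 14.7 says "There will be no data monitoring committee"; section 13.3 provides for no auditing and section 10 for no interim analysis.

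**The concern.** An event enters a count only if someone is in a position to hear of it and has somewhere to write it down. Under this plan both conditions differ by arm or are unspecified. A brief worsening in week three of AET would probably surface at a session within days. The same worsening in SC would have to be remembered and volunteered weeks later, because no visit asks for it.

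The results are to be published and presented to health professionals (14.9, 14.10). A statement that AET was or was not tolerated as well as standard care is a natural one to make, and worsening with exercise is the plan's own named risk. If the arms were equally safe, the arm observed more often would tend to show more events. The opposite error is also possible: if stopped sessions are never written down, real worsening under AET drops out of the record. Equal questioning cannot be recreated once follow-up is over.

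**Working it through.** **Inputs from the documents.** Eight weeks and three sessions per week (5.4, 7.2); 20 participants per group (5.2); four assessment sessions, A to D, before and after (7.1); no SC study contact listed between them (5.1, 6.4, 7.1).

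**The plan's own figure.** 8 x 3 = 24 sessions, which reproduces the number in 7.2.

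**Scheduled contacts per participant, from first pre assessment to last post assessment.**
- AET: 4 + 24 + 4 = 32.
- SC: 4 + 0 + 4 = 8.
- Between assessments only: 24 against 0, or 20 x 24 = 480 participant-sessions in AET against none in SC.

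**Section 13 beside 16.4.** Section 13 says each intervention visit is documented on the data abstraction form. The form has one assessment date, the first, and nothing that could record any of the 24 sessions, whether one was stopped, or an event. These two sections do not agree, and no assumption is needed to see it.

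**Illustration of the bias (assumed inputs).** The documents give no event risk and no capture fraction. Let p be the true risk of at least one event over eight weeks, equal in both arms, and let cA and cS be the fractions captured. The expected spurious difference is 20 x p x (cA - cS). With cA = 1:

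| p | cS | Expected AET | Expected SC | Spurious excess in AET | Chance that a two-sided Fisher test gives p at or below 0.05 |
|---|---|---|---|---|---|
| 10% | 0 | 2 | 0 | 2 | 4% |
| 10% | 0.5 | 2 | 1 | 1 | 2% |
| 10% | 1 | 2 | 2 | 0 | 1% |
| 20% | 0 | 4 | 0 | 4 | 37% |
| 20% | 0.5 | 4 | 2 | 2 | 7% |
| 20% | 1 | 4 | 4 | 0 | 2% |
| 30% | 0 | 6 | 0 | 6 | 76% |
| 30% | 0.5 | 6 | 3 | 3 | 12% |
| 30% | 1 | 6 | 6 | 0 | 2% |

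The sign depends on cA - cS. If stopped sessions went largely unrecorded, say cA = 0.25 and cS = 0.5 with p = 20%, the expected counts would be 20 x 0.2 x 0.25 = 1 in AET and 20 x 0.2 x 0.5 = 2 in SC, and AET would look safer than it is. The table shows how the bias works and does not estimate it. When capture is equal, the spurious difference is zero at every p.

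**Can events reach those who may terminate?** The chance that at least one of 20 AET participants has an event is 1 - (1 - p)^20: 64% at p = 5%, 88% at 10% and 99% at 20%. Staff are present at the sessions, so events that surface there would be seen as they happen.

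**The case against.** There is a fair case on the other side, and much of it stands.

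- No harms comparison is planned. Sections 10 and 11.2 analyse ERP, balance, BDNF, ImPACT scores and reaction time. A reader might infer that a planned comparison is biased, but the documents contain none. This stands, and makes the point conditional.
- A reader might infer that the adverse-event reason in 12.4 cannot operate, or that nobody reviews events. The text does not support that. The sponsor/investigator and the ethics board may terminate at any time, 14.8 routes events to the board, and AET events are visible to staff. What is missing is a cumulative log and a designated reviewer. The absence of a monitoring committee in a 60-person exercise study that rates its own risk as small is largely a matter of judgement.
- SC events are not excluded. The promise in 14.8 covers every arm, and SC participants can volunteer events at the four post sessions. The gap is unequal solicitation.
- SCAT-3 and RPSQ, named under hypothesis 1, would register lasting worsening alike in both arms if given. They have no row in 7.1, however, and two time points would miss episodes that resolve in between.
- The 16.4 form also lacks fields for test results, which sections 8.1 and 8.2 store elsewhere, so a missing event field does not prove that no log exists. A log required under ethics board guidelines would not be visible here, and the consent materials were not available for review. The mismatch between section 13 and 16.4 over intervention visits remains.

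**Conclusion.** The point holds in conditional form. The documents establish 24 monitored contacts against none scheduled, no adverse-event row in 7.1, a form that cannot hold the visits section 13 assigns to it, and no designated reviewer. Any AET versus SC summary of adverse events or symptom worsening would therefore be open to ascertainment bias. The likelier direction is against AET, because it is observed far more often; under-recording of stopped sessions could reverse it.

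A reader might want a specific number of excess events. The documents do not support one: every count in the illustration rests on an assumed risk and assumed capture fractions. The planned efficacy analyses are unaffected. The change is still worth making before enrolment, because it is cheap and the data cannot be recovered afterwards.

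**What to change.** 1. In 7.1 and 8.1, add one identical adverse-event and symptom-change question for AET and SC on the same schedule: at minimum at the post assessment, preferably also by a brief e-form at equal intervals. Ask HC at post. State that any between-arm harms summary uses this question alone.
2. In 16.4, add an event log and a per-session line (date, completed or stopped, reason), so that the form matches section 13. Report stopped sessions separately, as AET tolerability.
3. In 12.4 or 14.8, name a role that reviews the log and refers events to the ethics board. Do this outside the monthly team meetings, which the budget notes in 16.6 also assign to data analysis and interpretation, and apart from the analysts blinded under 12.3, since the log would reveal the arm. Any stopping criterion is for the investigators and the ethics board to set.

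Cost: schedule and form wording, a short e-form to about 40 people (20 AET + 20 SC) if the preferred option is taken, minor participant burden, and a little extra data handling. The e-form adds slight contact to an arm meant to continue usual care; asking only at the post assessment avoids this but relies on eight-week recall.

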14.9 Publication of Data and Protection of Trade Secrets

The results from this study will be published in a peer-reviewed scientific journal as aggregate data. The research team will have access to all coded data until the storage period is complete.

14.10 Dissemination

Participants can inquire about his/her own as well as aggregate study results. Aggregate data will be communicated to healthcare professionals and the public via presentations at local scientific conferences (such as the Northern Health Research Conference, Northern Constellations, or the Showcase of Healthcare Research) and a publication in a peer-reviewed scientific journal.

All research team members who have contributed intellectual input into the study design and/or interpretation of results, or contributed to data collection and/or analysis will be included as authors. Members of the research team will write any manuscripts resulting from the study.

16. APPENDICES

16.1 Recruitment materials

Do you have symptoms related to a concussion?

Help local researchers examine the effects of exercise on persistent symptoms

Who can participate?

- Adults between 18 and 50 years
- Fluent in English
- No history of neurological disorder
- 2 weeks to 6 months since injury
- Drivers license
- Not currently seeking counselling/therapy for depression

Contact us for more information!

[contact]

[name]
Assistant Professor
Lakehead University

For more Information about your rights as a research participant, contact the TBRHSC Ethics Board Chair at [name]

Are you a healthy individual with no concussion symptoms?

Help local researchers examine the effects of exercise on persistent symptoms

Who can participate?

- Adults between 18 and 50 years
- Fluent in English
- No history of neurological disorder
- Drivers license
- Not currently seeking counselling/therapy for depression

Contact us for more information!

[contact]

[name]
Assistant Professor
Lakehead University

For more Information about your rights as a research participant, contact the TBRHSC Ethics Board Chair at [name]

16.2 Informed consent materials

16.3 Screening checklists

Inclusion/Exclusion Criteria Screening Checklist- PCS

Participant number _____

- Person aged 18-50 years
- Fluent in English
- Experience injury greater than 2 weeks ago?
- Experienced injury less than 6 months ago?
- Not diagnosed with psychological/neurological disorder
- Not diagnosed with depression
- Not currently seeking counselling/therapy for depression
- Has valid drivers license with 12 months driving experience

Inclusion/Exclusion Criteria Screening Checklist- HC

Participant number _____

- Person aged 18-50 years
- Fluent in English
- Not diagnosed with psychological/neurological disorder
- Not diagnosed with depression
- Not currently seeking counselling/therapy for depression
- Has valid drivers license with 12 months driving experience

16.4 Data abstraction form

Participant Number: _____

Consent Date:

| | |
|--------------------------|--|
| Sex (male/female) | |
| Height (cm) | |
| Weight (kg) | |
| Age (in years) | |
| | |
| Date of injury | |
| Date of first assessment | |

Past Medical History

- Concussion
- Traumatic brain injury
- Migraine
- ADHD
- Motion sickness

(Y/N)

| |
|--|
| |
| |
| |
| |
| |

How many?

| |
|--|
| |
|--|

16.5 International Physical Activity Questionnaire

INTERNATIONAL PHYSICAL ACTIVITY QUESTIONNAIRE (August 2002)

SHORT LAST 7 DAYS SELF-ADMINISTERED FORMAT

FOR USE WITH YOUNG AND MIDDLE-AGED ADULTS (15-69 years)

The International Physical Activity Questionnaires (IPAQ) comprises a set of 4 questionnaires. Long (5 activity domains asked independently) and short (4 generic items) versions for use by either telephone or self-administered methods are available. The purpose of the questionnaires is to provide common instruments that can be used to obtain internationally comparable data on health-related physical activity.

Background on IPAQ

The development of an international measure for physical activity commenced in Geneva in 1998 and was followed by extensive reliability and validity testing undertaken across 12 countries (14 sites) during 2000. The final results suggest that these measures have acceptable measurement properties for use in many settings and in different languages, and are suitable for national population-based prevalence studies of participation in physical activity.

Using IPAQ

Use of the IPAQ instruments for monitoring and research purposes is encouraged. It is recommended that no changes be made to the order or wording of the questions as this will affect the psychometric properties of the instruments.

Translation from English and Cultural Adaptation

Translation from English is supported to facilitate worldwide use of IPAQ. Information on the availability of IPAQ in different languages can be obtained at www.ipaq.ki.se. If a new translation is undertaken we highly recommend using the prescribed back translation methods available on the IPAQ website. If possible please consider making your translated version of IPAQ available to others by contributing it to the IPAQ website. Further details on translation and cultural adaptation can be downloaded from the website.

Further Developments of IPAQ

International collaboration on IPAQ is on-going and an *International Physical Activity Prevalence Study* is in progress. For further information see the IPAQ website.

More Information

More detailed information on the IPAQ process and the research methods used in the development of IPAQ instruments is available at www.ipaq.ki.se and Booth, M.L. (2000). *Assessment of Physical Activity: An International Perspective*. Research Quarterly for Exercise and Sport, 71 (2): s114-20. Other scientific publications and presentations on the use of IPAQ are summarized on the website.

SHORT LAST 7 DAYS SELF-ADMINISTERED version of the IPAQ. Revised August 2002.

INTERNATIONAL PHYSICAL ACTIVITY QUESTIONNAIRE

We are interested in finding out about the kinds of physical activities that people do as part of their everyday lives. The questions will ask you about the time you spent being physically active in the **last 7 days**. Please answer each question even if you do not consider yourself to be an active person. Please think about the activities you do at work, as part of your house and yard work, to get from place to place, and in your spare time for recreation, exercise or sport.

Think about all the **vigorous** activities that you did in the **last 7 days**. **Vigorous** physical activities refer to activities that take hard physical effort and make you breathe much harder than normal. Think *only* about those physical activities that you did for at least 10 minutes at a time.

1. During the **last 7 days**, on how many days did you do **vigorous** physical activities like heavy lifting, digging, aerobics, or fast bicycling?

_____ **days per week**

No vigorous physical activities → **Skip to question 3**

2. How much time did you usually spend doing **vigorous** physical activities on one of those days?

_____ **hours per day**

_____ **minutes per day**

Don't know/Not sure

Think about all the **moderate** activities that you did in the **last 7 days**. **Moderate** activities refer to activities that take moderate physical effort and make you breathe somewhat harder than normal. Think *only* about those physical activities that you did for at least 10 minutes at a time.

3. During the **last 7 days**, on how many days did you do **moderate** physical activities like carrying light loads, bicycling at a regular pace, or doubles tennis? Do not include walking.

_____ **days per week**

No moderate physical activities → **Skip to question 5**

4. How much time did you usually spend doing **moderate** physical activities on one of those days?

_____ **hours per day**
_____ **minutes per day**

Don't know/Not sure

Think about the time you spent **walking** in the **last 7 days**. This includes at work and at home, walking to travel from place to place, and any other walking that you have done solely for recreation, sport, exercise, or leisure.

5. During the **last 7 days**, on how many days did you **walk** for at least 10 minutes at a time?

_____ **days per week**

No walking → **Skip to question 7**

6. How much time did you usually spend **walking** on one of those days?

_____ **hours per day**
_____ **minutes per day**

Don't know/Not sure

The last question is about the time you spent **sitting** on weekdays during the **last 7 days**. Include time spent at work, at home, while doing course work and during leisure time. This may include time spent sitting at a desk, visiting friends, reading, or sitting or lying down to watch television.

7. During the **last 7 days**, how much time did you spend **sitting** on a **week day**?

_____ **hours per day**
_____ **minutes per day**

Don't know/Not sure

This is the end of the questionnaire, thank you for participating.

SHORT LAST 7 DAYS SELF-ADMINISTERED version of the IPAQ. Revised August 2002.

